1 INTRODUCTION

This statistical analysis plan (SAP) defines the scope of statistical analyses and provides a detailed description of statistical methodology for the statistical analyses to support the final clinical study report (CSR). The SAP is based on the following study document: Protocol Amendment 2 29 Sep 2017.

2 PROTOCOL SUMMARY

RA0098 is a multicenter, open-label, Phase 3 study of the e-Device in US subjects with rheumatoid arthritis (RA), ankylosing spondylitis (AS), psoriatic arthritis (PsA), or Crohn's disease (CD).

The e-Device offers improved convenience with an enhanced, reusable electromechanical injector that provides full electronic management of the injection process including subject instructions and warnings via a graphical user interface, an electronic log of the injection history, and the speed of injection. The e-Device uses a disposable single-use certolizumab pegol (CZP) cassette/dose dispensing cartridge (henceforth referred to as CZP-cassette) which houses a (market authorized) pre-filled syringe (PFS) containing CZP 200mg. The CZP-cassette is needle-safe (ie, automatic needle retraction to prevent needle-stick injury), and, once loaded into the e-Device, is electronically recognized (ie, expiry date, drug identity, and use status) by the e-Device. The e-Device and CZP-cassette together provide automatic needle insertion, dose delivery, needle retraction, and adjustable injection speed. They also provide a manual voluntary injection pause and resumption for additional control as well as an automatic stop (with needle retraction) should the e-Device lose contact with the skin during an injection to prevent needle stick injury and to minimize the loss of CZP. A production version of the e-Device will be utilized for this study.

The purpose of this study is to determine whether the e-Device can be used safely and effectively for self-injection by subjects with RA, AS, PsA, or CD after being trained on proper self-injection technique. All eligible subjects should be currently treated with commercial CZP. Eligible subjects with RA, PsA, or AS will perform CZP self-administration a 2 week (Q2W) or 4 week (Q4W) dosing schedule. Eligible subjects with CD will perform CZP self-administration on a Q4W dosing schedule. As the dosing schedule groups (Q2W vs Q4W) are different regarding number of injections (1 CZP injection for Q2W vs 2 CZP injections per administration for Q4W) and study treatment period (2 weeks vs 4 weeks), these 2 subject populations will be evaluated separately. For simplicity and where appropriate, the RA, AS, and PsA subjects on the Q2W dosing regimen will be called the Q2W group, and the RA, AS, PsA, and CD subjects on the Q4W dosing regimen will be called the Q4W group.

The primary variable is the proportion (%) of subjects able to self-administer safe and effective injections using the e-Device at Visit 2. Safe and effective self-injection will be evaluated by the healthcare provider (HCP) and is defined as:

- Complete Dose Delivery: Subject self-injected the complete dose of CZP as confirmed by a visual inspection of the CZP-cassette(s) which shows the container PFS to be empty and

- No adverse events (AE) related to the use of the e-Device (adverse device effects [ADE]) that would preclude continued use of the e-Device for self-injection

Approximately 80 subjects ≥ 18 years of age who are currently being treated with commercial CZP, are self-injecting with the PFS, and are on a stable dosing regimen for at least 3 months will be screened in order to have at least 60 subjects use the e-Device at Visit 1. The 60 subjects using the e-Device at Visit 1 will be composed of a minimum of 15 subjects in each of the dosing groups (Q2W vs Q4W) with a minimum of 15 subjects with CD and a minimum of 10 subjects with impaired hand function.

2.1 Study objective(s)

2.1.1 Primary objective(s)

The primary objective of the study is to evaluate the ability of subjects in the Q2W and Q4W groups to safely and effectively self-inject certolizumab pegol (CZP) using the e-Device at Visit 2.

2.1.2 Secondary objective

The secondary objectives are to evaluate the ability of subjects in the Q2W and Q4W groups to safely and effectively self-inject CZP using the e-Device at Visit 1 and the structural integrity of used cassettes via visual examination.

2.1.3 Other objectives

The other objectives are to evaluate:

- The functional status of the e-Device following administration of the final study dose (ie, no visual signs of damage, device functions normally within training cassette)
- Subject experience of self-injection as assessed by the Pain Visual Analogue Scale (VAS) and Assessment of Self Injection (ASI)
- Subject preference for e-Device vs pre-filled syringe (PFS) using a self-administered Self-Injection Preference Questionnaire

2.1.4 Safety Objective

The safety objective is to evaluate the safety of CZP self-injection using the e-Device for CZP self-injection.

2.2 Study variables

2.2.1 Study outcome and variables

2.2.1.1 Primary outcome and variable

The primary outcome variable is the proportion (%) of subjects able to self-administer safe and effective injections using the e-Device at Visit 2. Safe and effective self-injection will be evaluated by the healthcare provider (HCP) and is defined as:

- Complete Dose Delivery: Subject self-injected the complete dose of CZP as confirmed by a visual inspection of the CZP-cassette(s) which shows the PFS container to be empty and

- No AEs related to use of the e-Device (ADEs) that would preclude continued use of the e-Device for self-injection

For subjects on the Q4W dosing regimen who will self-inject twice (2x200mg CZP) at each visit, each injection will be evaluated for safety and effectiveness using the above criteria. The primary endpoint of safe and effective self-injection for subjects on the Q4W dosing regimen will be met only if both self-injections are determined to be safe and effective.

2.2.1.2 Secondary outcome variables

The secondary variables are:

- The proportion (%) of subjects able to self-administer safe and effective injections using the e-Device at Visit 1. Safe and effective self-injection will be evaluated by the HCP and is defined as:
 - Complete Dose Delivery: Subject self-injected the complete dose of CZP as confirmed by a visual inspection of the CZP-cassette(s) which shows the PFS container to be empty and
 - No AEs related to use of the e-Device (ADEs) that would preclude continued use of the e-Device for self-injection

For subjects on the Q4W dosing regimen who will self-inject twice (2x200mg CZP) at each visit, each injection will be evaluated for safety and effectiveness using the above criteria. The primary endpoint of safe and effective self-injection for subjects on the Q4W dosing regimen will be met only if both injections are determined to be safe and effective.

- Percentage of used CZP-cassettes identified as having structural integrity issues based on visual examination (ie, clear evidence of damage/compromised structural integrity, not superficial cosmetic imperfections)

2.2.1.3 Other variables

The other outcome variables are:

- Injection site pain due to self-injection (using a VAS; 100mm) by visit at all visits after self-injection using e-Device

Subjects on the Q4W dosing regimen who will self-inject twice (2x200mg CZP) at each visit will complete the Pain VAS after the second injection at each of the 2 visits. For subjects on the Q4W dosing regimen, the Pain VAS will record the overall pain associated with both self-injections.

- Responses to the pre-injection Assessment of Self Injection (ASI) at Visit 1
- Responses to the post-injection ASI by visit at all visits after self-injection using the e-Device

Subjects on the Q4W dosing regimen who will self-inject twice (2x200mg CZP) at each visit will complete the post-injection ASI after the second injection at each of the 2 visits. For subjects on the Q4W dosing regimen, the post-injection ASI will collect the overall self-injection experience associated with both self-injections.

- Responses to the Self-Injection Preference Questionnaire

- In vitro functional evaluation of the e-Device following the final use per subject:
 - The percentage of e-Devices found to be functionally compromised (ie, visual signs of damage, device does not function normally with training cassette)

2.2.2 Safety variables

The safety variables are:

- Occurrence of AEs and ADEs
- Vital signs

2.3 Study design and conduct

In this Phase 3, open-label study of the e-Device, subjects diagnosed with RA, PsA, or AS (treated on a Q2W dosing schedule, Q2W group), or RA, PsA, AS, or CD (treated on a Q4W dosing schedule, Q4W group) will be recruited and evaluated. Subjects in the Q2W and Q4W group should currently be treated with commercial CZP and be performing self-administration using the PFS.

Hand function will be assessed at the screening visit by the Cochin Impaired Hand Function questionnaire. This study will recruit a minimum of 10 patients with impaired hand function. Impaired hand function will be measured using the Cochin scale and impaired hand function will be defined as patients who have a Cochin score ≥ 13.5 at baseline.

Participating subjects must be at least 18 years of age and on a stable CZP dosing regimen for at least 3 months before Visit 1.

Visit 1 should be scheduled to coincide with the individual treatment schedule for each subject. The study will consist of 2 site visits and a follow-up telephone call. Following an initial eligibility check at Visit 1, all eligible subjects will enter the Study Treatment Period at that same visit. Subjects will self-inject using the e-device immediately following training at Visit 1.

For subjects in the Q2W group, subjects will self-inject CZP 200mg using the e-Device (ie, 1x200mg injection). To meet the individual treatment schedule of the subjects, Visit 1 and Visit 2 should be consistent with their scheduled CZP dose (ie, 2 weeks between their last dose and Visit 1, and 2 weeks between Visit 1 and Visit 2).

For subjects in the Q4W group, subjects will self-inject CZP 400mg using the e-Device (ie, 2x200mg injections). To meet the individual treatment schedule of the subjects, Visit 1 and Visit 2 should be consistent with their scheduled CZP dose (ie, 4 weeks between their last dose and Visit 1, and 4 weeks between Visit 1 and Visit 2).

For both groups, a follow-up telephone call will be conducted 1 week after the final study drug administration as a safety follow-up call. Follow-up requirements for adverse events (Investigational Medicinal Product (IMP) and investigational device) and pregnancy are outlined in the protocol Sections 10.1.3, 10.2.3, and 10.3. Subjects who have a positive pregnancy test and who have self-administered at least 1 study dose of CZP who then discontinue CZP therapy will have a safety follow-up telephone call 70 days after the last study dose of CZP in addition to the 1-week Safety Follow-Up.

The study duration for each subject in the Q2W group on the Q2W dosing regimen is 3 weeks. The study duration for each subject in the Q4W group on the Q4W dosing regimen is 5 weeks.

Subjects will be required to perform a Safety Follow-Up by phone 1 week after their last study dose of CZP. Subjects who have a positive pregnancy test and who have self-administered at least 1 study dose of CZP who then discontinue CZP therapy will have a safety follow-up telephone call 70 days after the last study dose of CZP in addition to the 1-week Safety Follow-Up.

The end of study is defined as the date of the last telephone follow-up call for the last subject in the study.

2.3.1 Schedule of study assessment

Table 2-1: Schedule of study assessments for Q2W subjects

Assessments	Visit 1 (Week 0)		Visit 2 (Week 2) (±3 days)	Follow-Up ^a (Week 3) (±3 days)
	Screening	Study Treatment Period		
Written informed consent	X			
Demographic data	X			
Subject completes Cochin Impaired Hand Function questionnaire	X			
Verification of inclusion/exclusion criteria	X			
Withdrawal criteria				X
General medical/procedures history	X			
Physical examination ^b	X			
Vital signs ^c	X			X
Urine pregnancy test (βHCG) ^d	X			X
Contact IXRS	X			X
Recording of concomitant medication	X			X
Subject completes preinjection ASI		X		
Training with e-Device prior to self-administration		X		
Subject self-administers CZP using e-Device		X		X
HCP evaluates self-injection		X		X
Subject completes pain VAS (postinjection) ^e		X		X
Subject completes postinjection ASI ^f		X		X

Table 2–1: Schedule of study assessments for Q2W subjects

Assessments	Visit 1 (Week 0)		Visit 2 (Week 2) (±3 days)	Follow-Up ^a (Week 3) (±3 days)
	Screening	Study Treatment Period		
Assessment of structural integrity for CZP-cassette		X	X	
In vitro functional evaluation of e-Device			X	
Subject completes Self-Injection Preference Questionnaire			X	
Recording of AEs and ADEs		X	X	X

ADE=adverse device effect; AE=adverse event; AS=ankylosing spondylitis; ASI=Assessment of Self Injection; CZP=certolizumab pegol; HCP=healthcare provider; βHCG=beta human chorionic gonadotropin; IXRS=interactive response technology; Q2W=every 2 weeks; PsA=psoriatic arthritis; RA=rheumatoid arthritis; VAS=visual analog scale

Note: The visit window is ±3 days.

^a Subjects will be required to perform a Safety Follow-Up by phone 1 week after their last study dose of CZP. Subjects who are withdrawn from CZP treatment during the course of the study due to pregnancy will be required to perform a safety follow-up call 70 days following their final CZP administration in addition to the 1-week Safety Follow-Up.

^b Includes height and weight.

^c Includes blood pressure, pulse, body temperature, and respiratory rate.

^d For women of childbearing potential. A serum pregnancy test will be performed in the event of a positive urine result.

^e Immediately postinjection (within 15 minutes).

^f Within 30 minutes postinjection.

Table 2–2: Schedule of study assessments for Q4W subjects

Assessments	Visit 1 (Week 0)		Visit 2 (Week 4) (±3 days)	Follow-Up ^a (Week 5) (±3 days)
	Screening	Study Treatment Period		
Written informed consent	X			
Demographic data	X			
Subject completes Cochin Impaired Hand Function questionnaire	X			
Verification of inclusion/exclusion criteria	X			
Withdrawal criteria			X	

Table 2–2: Schedule of study assessments for Q4W subjects

Assessments	Visit 1 (Week 0)		Visit 2 (Week 4) (±3 days)	Follow-Up ^a (Week 5) (±3 days)
	Screening	Study Treatment Period		
General medical/procedures history	X			
Physical examination ^b	X			
Vital signs ^c	X		X	
Urine pregnancy test (βHCG) ^d	X		X	
Contact IXRS	X		X	
Recording of concomitant medication	X		X	
Subject completes preinjection ASI		X		
Training with e-Device prior to self-administration		X		
Subject self-administers CZP using e-Device		X	X	
HCP evaluates self-injection		X	X	
Subject completes pain VAS (postinjection) ^e		X	X	
Subject completes postinjection ASI ^f		X	X	
Assessment of structural integrity for CZP-cassette		X	X	
In vitro functional evaluation of e-Device			X	
Subject completes Self-Injection Preference Questionnaire			X	
Recording of AEs and ADEs	X		X	X

Table 2–2: Schedule of study assessments for Q4W subjects

Assessments	Visit 1 (Week 0)		Visit 2 (Week 4) (±3 days)	Follow-Up ^a (Week 5) (±3 days)
	Screening	Study Treatment Period		

ADE=adverse device effect; AE=adverse event; ASI=Assessment of Self Injection; CD=Crohn's disease; CZP=certolizumab pegol; HCP=healthcare practitioner; βHCG=beta human chorionic gonadotropin; IXRS=interactive response technology; Q4W=every 4 weeks; VAS=visual analog scale

Note: The visit window is ±3 days.

^a Subjects will be required to perform a Safety Follow-Up by phone 1 week after their last study dose of CZP. Subjects who are withdrawn from CZP treatment during the course of the study due to pregnancy will be required to perform a safety follow-up call 70 days following their final CZP administration in addition to the 1-week Safety Follow-Up.

^b Includes height and weight.

^c Includes blood pressure, pulse, body temperature, and respiratory rate.

^d For women of childbearing potential. A serum pregnancy test will be performed in the event of a positive urine result.

^e Immediately postinjection (within 15 minutes).

^f Within 30 minutes postinjection.

2.4 Determination of sample size

This study will not be powered with respect to any endpoint and sample size is based on practical considerations. The number of subjects and their diagnosed conditions are summarized below.

Approximately 80 subjects who are currently being treated with commercial CZP and are on a stable dosing regimen for at least 3 months will be screened in order to have at least 60 subjects use the e-Device at Visit 1. The 60 subjects using the e-Device at Visit 1 will be composed of a minimum of 15 subjects in each of the dosing groups (Q2W vs Q4W) with a minimum of 15 subjects with CD and a minimum of 10 subjects with impaired hand function. Impaired hand function will be measured using the Cochin scale (Poiraudieu et al, 2000; Duruöz et al, 1996) and impaired hand function will be defined as patients who have a Cochin score ≥13.5 at baseline.

3 DATA ANALYSIS CONSIDERATIONS

3.1 General presentation of summaries and analyses

This is an estimation study design with no formal statistical hypothesis testing. All statistical analysis will be descriptive in nature. No inferential analyses are planned.

The study will estimate the true proportion and/or mean. Each endpoint will be summarized overall and by dosing group (Q2W or Q4W) and indication (RA, PsA, AS or CD).

Statistical analysis and generation of tables, figures, subject data listings, and statistical output will be carried out using SAS® Version 9.3 or higher.

Summary statistics for continuous variables will include the number of subjects with available measurement (n), mean, standard deviation (SD), median, minimum value, and maximum value.

For categorical variables, the number and proportion of subjects, along with the 90% confidence interval (CI) based on the Exact Binomial method, will be presented.

Decimal places for descriptive statistics will always apply the following rules:

“n” will be an integer.

Mean, SD and median will use 1 additional decimal place compared to the original data.

Minimum and maximum will have the same number of decimal places as the original value.

Unless otherwise noted, all proportions will be displayed to 1 decimal place. No proportion will be displayed for zero counts, and no decimal will be presented when the proportion is 1.

No imputation of missing data will be performed.

All data recorded in the eCRF and questionnaires will be listed.

3.2 Analysis time points

3.2.1 Relative day

Relative day 1 is the date of first certolizumab pegol (CZP) administration via e-Device.

Relative day of date X = date X - Date of first CZP administration+1 if date X is on or after date of first CZP administration.

Relative day of date X = date X - Date of first CZP administration if date X is before date of first CZP administration.

Relative days before first administration of CZP will have the prefix “-“.

Relative day after last dose will have the prefix “+”, and will be calculated from the date of last CZP administration (date X - date of last CZP administration+1). Relative day after last dose should typically only be calculated for the safety follow-up visit.

Calculations of “Relative Day” should not include partial dates, but should be left blank in these instances.

3.2.2 Mapping of assessments performed at Early Discontinuation Visit

Assessments at an Early Discontinuation Visit (EDV) that correspond to a scheduled visit will be summarized at the scheduled visit corresponding to the EDV if the assessment was scheduled to occur at that visit. Such assessments will also be considered for Last Value.

In particular, vital signs and body weight are assessed at all Treatment Period visits, and so all assessments of these variables at EDVs corresponding to a scheduled visit will be mapped to the corresponding scheduled visit. If such assessment occurs at an unscheduled visit, it will be mapped to the next scheduled visit.

3.3 Definition of Baseline values

A Baseline value for a subject is defined as the latest non-missing measurement prior to self-injection at Visit 1.

3.4 Protocol deviations

Important protocol deviations are deviations from the protocol which potentially could have a meaningful impact on the primary objective of the study. The criteria for identifying important protocol deviations and the classification of important protocol deviations will be defined within the Data Cleaning Plan. To the extent feasible the rules for identifying protocol deviations will be defined without review of the data and without consideration of the frequency of occurrence of such deviations. Whenever possible, criteria for identifying important protocol deviations will be implemented algorithmically to ensure consistency in the classification of important protocol deviations across all subjects.

3.5 Analysis sets

3.5.1 Safety Set

The Safety Set (SS) will consist of all subjects of the study who have received at least 1 dose of CZP during the study (e-Device).

3.5.2 Full Analysis Set

The Full Analysis Set (FAS) will consist of all subjects in the SS who received at least 1 dose of CZP using the e-Device in the study.

Since SS and FAS have the same definition in this study, the two sets will contain the same population. SS will be used for analyzing both safety variables and outcome variables in all presentations.

3.6 Treatment assignment and treatment groups

At Visit 1 and Visit 2, subjects on Q2W dosing regimen will self-inject CZP 200mg (1x200mg injection) using the e-Device. At Visit 1 and Visit 2, subjects on Q4W dosing regimen will self-inject CZP 400mg (2x200mg injections) using the e-Device. The actual dosing groups Q2W and Q4W will be used in presentation in the Tables, Figures and Listings (TFLs).

3.7 Center pooling strategy

Not applicable.

3.8 Coding dictionaries

Medical history and adverse events (AEs) will be coded using the Medical Dictionary for Regulatory Activities (MedDRA 19.0). Medications will be coded using the World Health Organization Drug Reference List (WHO-DRL SEP/2015). Medical procedures will not be coded.

3.9 Changes to protocol-defined analyses

Not applicable.

4 STATISTICAL/ANALYTICAL ISSUES

This is an estimation study design with no formal statistical hypothesis testing. The study will estimate the true population proportion and/or mean for the outcome variables. Each endpoint will be summarized overall and by dosing group (Q2W or Q4W) and indication.

Summary statistics for continuous variables will include:

- Number of available observations
- Mean, standard deviation, minimum, median, and maximum

For categorical variables, the number and proportion of subjects, along with the 90% confidence interval (CI) based on the Exact Binomial method, will be presented.

No imputation of missing data will be performed unless otherwise specified.

All data recorded in the eCRF and questionnaires will be listed by dosing group and indication within dosing group.

4.1 Adjustments for covariates

Not applicable.

4.2 Handling of dropouts or missing data

In the case of missing or partially missing dates, imputation rules for adverse events and medications shall be applied, so that concomitance (for medications) and treatment emergence (for adverse events) can be determined. Such imputations will only be performed for these classifications and calculations; in the listings all data will be shown as recorded on the eCRF.

4.2.1 Handling of prior and concomitant medications with missing data

Any medications with incomplete start and end dates/times will be handled according to the following rules for classification as prior and concomitant and for the calculation of relative study days. Such imputations will only be performed for these classifications and calculations; in the listings all data will be shown as recorded on the eCRF.

Imputation of Partial Start Dates:

- If only the month and year are specified and the month and year of first dose is not the same as the month and year of the start date, then use the 1st of the month.
- If only the month and year are specified and the month and year of first dose is the same as the month and year of the start date, then use the date of first dose.
- If only the year is specified, and the year of first dose is not the same as the year of the start date, then use January 1 of the year of the start date.
- If only the year is specified, and the year of first dose is the same as the year of the start date, then use the date of first dose.
- If the date is completely unknown, then use the date of first dose.

Imputation of Partial End Dates:

- If only the month and year are specified then use the last day of the month.

- If only the year is specified then use December 31 of that year.
- If the date is completely unknown, do not impute the stop date.

There will be no imputation of any other missing data.

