6.4 Prior and concomitant medications

Prior medications include any medications that started prior to the start date of study medication. Past medications are a subset of prior medications, and include prior medications with a stop date before the date of first CZP administration via e-Device. Concomitant medications are medications taken at least one day in common with the study medication dosing period. For this study, that will include from the date of first self-administration of CZP via e-Device up to the SFU visit.

In the case of missing data, the classification of medications as prior and/or concomitant will be performed as described in [Section 4.2.2](#). Imputations of missing data will be performed before calculation of relative study days.

The number and percentage of subjects taking prior medications will be summarized overall and by dosing group and indication, and by anatomical therapeutic chemical (ATC) class, presenting Anatomical Main Group (ATC Level 1), and PT. The number and percentage of subjects taking concomitant medications will be summarized similarly. Tables for prior and concomitant medications will be presented for the SS.

Prior and concomitant medications will be listed by dosing group and indication within dosing group for the SS. Prior and concomitant procedures will be listed for reported term by dosing group and indication within dosing group.

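### Medication starts imputed to the first-dose date can never count as prior, so a drug stopped before first dose can fall into neither medication table

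*SAP*

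**What the plan says.** SAP 4.2.1 states that its imputed dates serve to classify drugs as prior and concomitant. Three of its start-date rules lead to the date of first dose:

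- Start completely unknown: "If the date is completely unknown, then use the date of first dose".
- Only the year known: if "the year of first dose is the same as the year of the start date, then use the date of first dose".
- Only the month and year known, and equal to those of first dose: also the date of first dose (the rule opening "If only the month and year are specified and the month and year of first dose is the same as the month and year of").

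A start known to a different year becomes 1 January of that year, and one known to a different month becomes the 1st of that month.

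For stop dates: "If only the month and year are specified then use the last day of the month"; a stop known only to the year becomes 31 December; and "If the date is completely unknown, do not impute the stop date".

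SAP 6.4 then defines the categories: "Prior medications include any medications that started prior to the start date of study medication". Past drugs are those prior drugs that stopped before the first e-Device dose. Concomitant drugs overlap, by a day or more, the period from the first e-Device dose to the safety follow-up. Tables are planned for prior and for concomitant drugs only. For missing data, 6.4 says "the classification of medications as prior and/or concomitant will be performed as described in" Section 4.2.2, which is the adverse-event section.

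**The concern.** Moving an unknown date to first dose is cautious for adverse events, because it makes the event treatment-emergent. It is also cautious for concomitance. For the prior classification it works the other way: prior requires a start strictly before first dose, and the rule assigns a start equal to first dose. No drug given that imputed date can be prior, whatever its history.

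Nothing in 4.2.1 compares the imputed start with the stop. A drug known to have ended before Visit 1 can therefore be given a start after its own end and drop out of both planned tables. At stake is whether the prior-medication table correctly describes the subjects' background treatment.

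**Working it through.** No sample size, power or alpha figure bears on this, and the plan states no figure to reproduce. The check applies the rules of SAP 4.2.1 and the definitions of SAP 6.4 literally to test records.

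Let F be the date of first dose and S the safety follow-up. SAP 4.2.1 does not define first dose; it is read here as the first e-Device dose, in line with SAP 3.2.1 and 6.4.

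- prior: start < F
- past: prior and stop < F
- concomitant: start ≤ S, and stop missing or stop ≥ F

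The dates are illustrative assumptions: F = 20 Nov 2017, S = 11 Dec 2017. Only the order of the dates matters.

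| Start recorded | Stop recorded | Start used | Stop used | Prior | Past | Concomitant |
|---|---|---|---|---|---|---|
| unknown | ongoing | 20 Nov 2017 | none | no | no | yes |
| unknown | 15 Sep 2017 | 20 Nov 2017 | 15 Sep 2017 | no | no | no |
| unknown | Oct 2017 | 20 Nov 2017 | 31 Oct 2017 | no | no | no |
| unknown | 2016 | 20 Nov 2017 | 31 Dec 2016 | no | no | no |
| unknown | Nov 2017 | 20 Nov 2017 | 30 Nov 2017 | no | no | yes |
| 2017 | ongoing | 20 Nov 2017 | none | no | no | yes |
| 2017 | 30 Jun 2017 | 20 Nov 2017 | 30 Jun 2017 | no | no | no |
| Nov 2017 | 5 Nov 2017 | 20 Nov 2017 | 5 Nov 2017 | no | no | no |
| 2010 | ongoing | 1 Jan 2010 | none | yes | no | yes |
| Mar 2017 | 30 Jun 2017 | 1 Mar 2017 | 30 Jun 2017 | yes | yes | no |

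The five rows with no in all three columns are in no table, and in each the start used is later than the stop used. In each the drug must have begun before F, because it ended before F. The last two rows are controls: a start known to an earlier year or month is classified as intended.

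With the imputed start capped at the stop, the same five records get starts of 15 Sep 2017, 31 Oct 2017, 31 Dec 2016, 30 Jun 2017 and 5 Nov 2017. All are before F, so all become prior and past.

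For scale, the prior table counts subjects. If one subject is lost from a drug class, the overall percentage falls by at most 1/60 = 1.7 points (planned minimum of 60 subjects). In a dosing group at its minimum of 15 it falls by 1/15 = 6.7 points. A subject with another correctly dated drug in the same class is still counted in that class.

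**The case against.** The strongest reply is that few such records may exist. The protocol's schedules of assessments ask only for concomitant medication to be recorded, and Protocol 7.8.1 does the same; neither asks for a history of discontinued drugs. That stands as a limit on the number. It does not remove the point, because SAP 6.4 defines past drugs and plans a prior table, so the SAP expects some such records.

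Second, SAP 4.2 gives the purpose of imputing medication dates as settling concomitance, and for that the rule works. True, but 4.2.1 also names the prior classification.

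Third, ongoing drugs stay in the concomitant table and the listings show dates as recorded. Both stand, and they keep the point minor.

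Fourth, the reference to 4.2.2 looks editorial. Its start-date rules are the same, so the gap exists under either section; but 4.2.2 imputes no end dates, so following 6.4 literally would lose the stop-date rules of 4.2.1.

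Stronger readings are tempting but unsupported:

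- A reader might infer that every record imputed to first dose is misclassified. A drug that really began on or after first dose is correctly left out of prior, and some recorded only by month or year may be of that kind.
- A reader might infer that older treatments suffer most. One with a known earlier year is classified correctly; only a start with no year at all is affected.
- A reader might assume a share of undated records and take it as the table's shortfall. The documents give no such share, and the table counts subjects, not records.

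**Conclusion.** The rule and the definition conflict, and the result is deterministic. A drug with a completely unknown, same-year-only or same-month-only start and a stop before first dose is left out of both planned tables, although its stop date shows it was prior. An ongoing drug with a completely unknown start is shown as concomitant only.

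The point is minor. It affects one descriptive table, and the number of affected subjects cannot be computed from the documents. A reader might infer some effect on the study's results; there is none. The SAP makes no covariate adjustment, prior medication is neither a subgroup nor part of an analysis-set definition, and all analyses are descriptive.

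The conclusion assumes that first dose means the first e-Device dose, which is the only reading the SAP supports.

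**What to change.** In SAP 4.2.1:

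- State that an imputed start may not be later than the recorded or imputed stop, so that any drug stopped before first dose is prior (past).
- Class a drug with a completely unknown start as prior, and also as concomitant unless it stopped before first dose.
- Leave the same-month and same-year rules as they are apart from this cap. Classing all such partial starts as prior would wrongly include drugs begun after Visit 1.

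In SAP 6.4, change the cross-reference from 4.2.2 to 4.2.1.

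The cost is SAP wording and a few lines of code, with nothing for sites. The small downside is that a few drugs with a completely unknown start that in fact began on study would be counted as prior as well as concomitant.
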